**RESTRICTED**

DOCUMENT REF.: SOP-ST-01 LAST REVISION DATE: N/A VERSION NO.: 1.0	DOCUMENT NAME: Statistical Analysis Plan			
	SPONSOR: Scandinavian Biopharma Holding AM (SBH)	PROTOCOL NUMBER: OEV-131	PROTOCOL TITLE: Pre-Study of wild type Enterotoxigenic E.coli (ETEC) Strain for Verification of a planned Challenge Dose	VERSION NO: 1.0 VERSION DATE: 14JUN2024

**RESTRICTED**

DOCUMENT REF.: SOP-ST-01 LAST REVISION DATE: N/A VERSION NO.: 1.0	DOCUMENT NAME: Statistical Analysis Plan			
	SPONSOR: Scandinavian Biopharma Holding AM (SBH)	PROTOCOL NUMBER: OEV-131	PROTOCOL TITLE: Pre-Study of wild type Enterotoxigenic E.coli (ETEC) Strain for Verification of a planned Challenge Dose	VERSION NO: 1.0 VERSION DATE: 14JUN2024

## 10.1 Disposition of Subjects

Figure 1: CONSORT Flow Diagram

**RESTRICTED**

SPONSOR:  
Scandinavian  
Biopharma  
Holding AM (SBH)

PROTOCOL  
NUMBER:  
OEV-131

PROTOCOL TITLE:  
Pre-Study of wild type Enterotoxigenic  
*E.coli* (ETEC) Strain for Verification of a  
planned Challenge Dose

VERSION NO:  
1.0  
VERSION DATE:  
14JUN2024

## 14.2 Clinical Data

**Figure 2: Time to Primary Endpoint and Unadjudicated Primary Endpoint - Full Analysis Set**

[figure not shown]

Figure with similar format:

**Figure 3: Time to Primary Endpoint Sensitivity Analysis - Full Analysis Set**

[Implementation Note: This figure will display only one curve for time to primary endpoint, with subjects who met the primary endpoint but did not meet the stool frequency and weight criteria having event time imputed as 120 hours post challenge.]

**Figure 4: Time to Diarrhea Onset - Full Analysis Set**

[Implementation Note: This figure will display only one curve for diarrhea onset.]

[figure not shown]
**RESTRICTED**

	SPONSOR: Scandinavian Biopharma Holding AM (SBH)	PROTOCOL NUMBER: OEV-131	PROTOCOL TITLE: Pre-Study of wild type Enterotoxigenic E.coli (ETEC) Strain for Verification of a planned Challenge Dose	VERSION NO: 1.0
				VERSION DATE: 14JUN2024

#### 14.3 Safety Data

**Figure 5: Maximum Severity of ETEC Diseases-Specific Solicited Events by Sign or Symptom - Full Analysis Set**

[figure not shown]
[Implementation Note: A generic sample figure is shown below. The bar chart should be presented in a single-paneled figure labeled as “All Subjects (N=X)”, where N = the number of subjects in the Full Analysis Set. Axes should be labeled as follows: y-axis label: Sign or Symptom, x-axis label: Percentage of Subjects (%). Subjects are counted at most once per sign or symptom at the maximum severity reported.]

SPONSOR: Scandinavian Biopharma Holding AM (SBH)	PROTOCOL NUMBER: OEV-131	PROTOCOL TITLE: Pre-Study of wild type Enterotoxigenic E.coli (ETEC) Strain for Verification of a planned Challenge Dose	VERSION NO: 1.0
			VERSION DATE: 14JUN2024

**Figure 6: Number of Unsolicited Adverse Events by MedDRA System Organ Class and Severity - Full Analysis Set**

[Implementation Note: A generic sample figure is shown below. The figure can be shaded with the default coloring instead of the patterns. The bar chart should be presented in a single-paneled figure labeled as "All Subjects (N=X)", where N = the number of subjects in the Full Analysis Set. Axes should be labeled as follows: y-axis label: System Organ Class, x-axis label: Number of Events.]

[figure not shown]

**RESTRICTED**

SPONSOR: Scandinavian Biopharma Holding AM (SBH)	PROTOCOL NUMBER: OEV-131	PROTOCOL TITLE: Pre-Study of wild type Enterotoxigenic E.coli (ETEC) Strain for Verification of a planned Challenge Dose	VERSION NO: 1.0
			VERSION DATE: 14JUN2024

**Figure 7: Percentage of Subjects Reporting Unsolicited Adverse Events by MedDRA® System Organ Class and Maximum Severity - Full Analysis Set**

[Implementation Note: A generic sample figure is shown below. The figure can be shaded with the default coloring instead of the patterns. The bar chart should be presented in a single-paneled figure labeled as “All Subjects (N=X)”, where N = the number of subjects in the Full Analysis Set. Axes should be labeled as follows: y-axis label: System Organ Class, x-axis label: Percent of Subjects (%). Subjects are counted at most once at the maximum severity across for any events in the applicable SOC.]

	SPONSOR: Scandinavian Biopharma Holding AM (SBH)	PROTOCOL NUMBER: OEV-131	PROTOCOL TITLE: Pre-Study of wild type Enterotoxigenic E.coli (ETEC) Strain for Verification of a planned Challenge Dose	VERSION NO: 1.0

**Figure 8: Number of Unsolicited Adverse Events by MedDRA System Organ Class and Relationship to Challenge - Full Analysis Set**

[This figure will be similar to Figure 6. Bars will be categorized by relationship to challenge instead of severity.]

**Figure 9: Percentage of Subjects Reporting Unsolicited Adverse Events by MedDRA System Organ Class and Maximum Relationship to Challenge - Full Analysis Set**

[This figure will be similar to Figure 7. Bars will be categorized by relationship to challenge instead of severity.]

**RESTRICTED**

SPONSOR: Scandinavian Biopharma Holding AM (SBH)	PROTOCOL NUMBER: OEV-131	PROTOCOL TITLE: Pre-Study of wild type Enterotoxigenic E.coli (ETEC) Strain for Verification of a planned Challenge Dose	VERSION NO: 1.0
			VERSION DATE: 14JUN2024

**RESTRICTED**

	SPONSOR: Scandinavian Biopharma Holding AM (SBH)	PROTOCOL NUMBER: OEV-131	PROTOCOL TITLE: Pre-Study of wild type Enterotoxigenic E.coli (ETEC) Strain for Verification of a planned Challenge Dose	VERSION NO: 1.0

#### 16.2.5 Compliance and/or Drug Concentration Data

##### Listing 1: Study Challenge Administration\*

Subject ID	Was Challenge Administered?	Date of Challenge Administration	Time of Challenge Administration	Did Subject Vomit after Challenge Administration?
XXXXXXX	Yes / No	DDMMYYYY	xx:xx	Yes / No / N/A

**RESTRICTED**

	SPONSOR: Scandinavian Biopharma Holding AM (SBH)	PROTOCOL NUMBER: OEV-131	PROTOCOL TITLE: Pre-Study of wild type Enterotoxigenic E.coli (ETEC) Strain for Verification of a planned Challenge Dose	VERSION NO: 1.0
				VERSION DATE: 14JUN2024

#### 16.2.4.1 Demographic Data

##### Listing 2: Demographic Data

[Implementation Note: If a subject is multi-racial, in “Race” column, note “Multiple: (list races, separated by a comma).”]

Subject ID	Sex	Age at Screening (years)	Ethnicity	Race	Height (cm)	Weight (kg)	BMI (kg/m  )

**RESTRICTED**

	SPONSOR: Scandinavian Biopharma Holding AM (SBH)	PROTOCOL NUMBER: OEV-131	PROTOCOL TITLE: Pre-Study of wild type Enterotoxigenic E.coli (ETEC) Strain for Verification of a planned Challenge Dose	VERSION NO: 1.0
				VERSION DATE: 14JUN2024

#### 16.2.1 Discontinued Subjects

##### **Listing 3: Early Terminations**

[Implementation Note: Category will be either “Early Termination” or “Treatment Discontinuation.” In the “Reason” column, concatenate any “specify” fields, including AE number and DV number.]

Subject ID	Category	Reason for Early Termination	Study Day

**RESTRICTED**

SPONSOR: Scandinavian Biopharma Holding AM (SBH)	PROTOCOL NUMBER: OEV-131	PROTOCOL TITLE: Pre-Study of wild type Enterotoxigenic E.coli (ETEC) Strain for Verification of a planned Challenge Dose	VERSION NO: 1.0
			VERSION DATE: 14JUN2024

#### 16.2.2.1 Subject-Specific Protocol Deviations

##### Listing 4: Subject-Specific Protocol Deviations

[Implementation Note: In the “Deviation” column, concatenate any and all “specify” fields (including visit number, etc.). If “Reason for Deviation” is “Other,” concatenate “specify” field, separate by a colon, e.g., “Other: Subject refusal.”]

Subject ID	DV Number	Deviation	Deviation Category	Major or Minor Deviation?	Study Day	Reason for Deviation	Deviation Resulted in AE?	Deviation Resulted in Subject Termination?	Deviation Affected Product Stability?	Deviation Resolution	Comments

**RESTRICTED**

	SPONSOR: Scandinavian Biopharma Holding AM (SBH)	PROTOCOL NUMBER: OEV-131	PROTOCOL TITLE: Pre-Study of wild type Enterotoxigenic E.coli (ETEC) Strain for Verification of a planned Challenge Dose	VERSION NO: 1.0
				VERSION DATE: 14JUN2024

#### 16.2.2.2 Non-Subject Specific Protocol Deviations

##### **Listing 5: Non-Subject-Specific Protocol Deviations**

[Implementation Note: In the “Deviation” column, concatenate any and all “specify” fields (including visit number, etc.). If “Reason for Deviation” is “Other,” concatenate “specify” field, separate by a colon, e.g., “Other: Subject refusal.” Sort by Start Date.]

Start Date	Deviation	End Date	Reason for Deviation	Deviation Resulted in Subject Termination?	Deviation Affected Product Stability?	Deviation Category	Deviation Resolution	Comments

**RESTRICTED**

	SPONSOR: Scandinavian Biopharma Holding AM (SBH)	PROTOCOL NUMBER: OEV-131	PROTOCOL TITLE: Pre-Study of wild type Enterotoxigenic E.coli (ETEC) Strain for Verification of a planned Challenge Dose	VERSION NO: 1.0
				VERSION DATE: 14JUN2024

## 16.2.6 Individual Clinical Data

### 16.2.6.1 Grade 3-5 Stool Output

#### Listing 6: Grade 3-5 Stool Output\*

[Implementation Note: The text in blue shows an example entry. Actual data should be presented in black text.]

Subject ID	Diarrhea Episode a No.	Grade 3-5 Stool No.	Time of Grade 3-5 Stool Relative to Challenge	Stool Weight	Stool Grade	Grade 3-5 Stools Passed within Previous 24 Hours	Total Number of Grade 3-5 Stools within Previous 24 Hours	Total Weight of Grade 3-5 Stools within Previous 24 Hours	Did Episode Meet Frequency and/or Weight Threshold for Primary Endpoint?	Did Episode Begin Prior to 120 Hours Post Challenge?	Did Subject Meet Unadjudicated Primary Endpoint? b	Did Subject Meet Primary Endpoint? c	Qualifying Information Provided by Adjudication Committee
xxxx	1	1	13 hrs, 2 min	105 g	5	Stool 1	1	105 g	Yes	Yes	Yes	Yes	-
		2	16 hrs, 14 min	232 g	5	Stools 1-2	2	337 g					
		3	29 hrs, 45 min	107 g	3	Stools 1-3	3	444 g					
		4	42 hrs, 29 min	52 g	2	Stools 3-4	2	159 g					
	2	1	105 hrs, 55 min	32 g	3	Stool 1	1	32 g	No	Yes	Yes	Yes	-
		2	122 hrs, 3 min	30 g	3	Stools 1-2	2	62 g					

Notes: Yellow highlighted cells indicate that the stool frequency or weight threshold for the primary endpoint has been met.

a A diarrhea episode starts when the first grade 3-5 stool that contributes to diarrhea of any severity is passed. A diarrhea episode ends when a subject has not passed any grade 3-5 stools within the past 24 hours.

b Moderate to severe diarrhea is defined as having a moderate and/or severe diarrhea episode beginning prior to 120 hours after challenge.

c The primary endpoint is defined as having a moderate and/or severe diarrhea episode or ETEC symptoms beginning prior to 120 hours after challenge, deemed attributable to ETEC as decided by an adjudication committee of experts in diarrheal illness.

RESTRICTED

DOCUMENT REF.: SOP-ST-01  
LAST REVISION DATE: N/A  
VERSION NO.: 1.0

DOCUMENT NAME:  
**Statistical Analysis Plan**

	SPONSOR: Scandinavian Biopharma Holding AM (SBH)	PROTOCOL NUMBER: OEV-131	PROTOCOL TITLE: Pre-Study of wild type Enterotoxigenic E.coli (ETEC) Strain for Verification of a planned Challenge Dose	VERSION NO: 1.0
				VERSION DATE: 14JUN2024

#### 16.2.6.2 Individual Data Contributing to ETEC Disease Severity Score

##### Listing 7: Individual Data Contributing to ETEC Disease Severity Score

Subject ID	Maximum # of Vomiting Episodes in 24- Hour Window	Fever?	Lightheaded- ness? (Severity)	Nausea? (Severity)	Malaise? (Severity)	Headache? (Severity)	Abdominal Cramps? (Severity)	Maximum # of Grade 3-5 Stools in 24-Hour Window	Maximum Weight of Grade 3-5 Stools in 24-Hour Window	ETEC Disease Severity Score
xxxxx	x	Yes/No	Yes/No (Severity)	Yes/No (Severity)	Yes/No (Severity)	Yes/No (Severity)	Yes/No (Severity)	x	xxx g	x

**RESTRICTED**

	SPONSOR: Scandinavian Biopharma Holding AM (SBH)	PROTOCOL NUMBER: OEV-131	PROTOCOL TITLE: Pre-Study of wild type Enterotoxigenic E.coli (ETEC) Strain for Verification of a planned Challenge Dose	VERSION NO: 1.0
				VERSION DATE: 14JUN2024

#### 16.2.6.3 Functional Bowel Disorder Survey

##### **Listing 8: Positive Responses to Functional Bowel Disorder Survey**

[Implementation Note: List only questions with at least one “positive” response, i.e. a response other than “No,” “Never,” etc. If a subject has a positive response at only one visit (screening or Day 180), still list the subject’s response at both visits.]

Subject ID	Question Category	Question	Response at Screening	Response at Day 180
xxxxx	Symptoms in the Esophagus / Symptoms of the Stomach and Intestines / Other	[Question 1]	Never / Less than one day a month / one day a month / Yes / No / etc.	Never / Less than one day a month / one day a month / Yes / No / etc.
xxxxx	Symptoms in the Esophagus / Symptoms of the Stomach and Intestines / Other	[Question 2]	Never / Less than one day a month / one day a month / Yes / No / etc.	Never / Less than one day a month / one day a month / Yes / No / etc.
xxxxx	Symptoms in the Esophagus / Symptoms of the Stomach and Intestines / Other	Continue with additional questions...	Never / Less than one day a month / one day a month / Yes / No / etc.	Never / Less than one day a month / one day a month / Yes / No / etc.

**RESTRICTED**

	SPONSOR: Scandinavian Biopharma Holding AM (SBH)	PROTOCOL NUMBER: OEV-131	PROTOCOL TITLE: Pre-Study of wild type Enterotoxigenic E.coli (ETEC) Strain for Verification of a planned Challenge Dose	VERSION NO: 1.0
				VERSION DATE: 14JUN2024

#### 16.2.4.2 Medical History

##### Listing 9: Medical History

[Implementation Note: “Condition Start Day” and “Condition End Day” are relative to enrollment (which is Day 1, day before enrollment is Day -1).]

Subject ID	MH Number	Medical History Term	Condition Start Day	Condition End Day	MedDRA System Organ Class	MedDRA Preferred Term

**RESTRICTED**

DOCUMENT REF.: SOP-ST-01 LAST REVISION DATE: N/A VERSION NO.: 1.0	DOCUMENT NAME: Statistical Analysis Plan				
	SPONSOR: Scandinavian Biopharma Holding AM (SBH)	PROTOCOL NUMBER: OEV-131	PROTOCOL TITLE: Pre-Study of wild type Enterotoxigenic E.coli (ETEC) Strain for Verification of a planned Challenge Dose		VERSION NO: 1.0
					VERSION DATE: 14JUN2024

#### 16.2.9.1 Prior and Concomitant Medications

##### Listing 10: Prior and Concomitant Medications

Subject ID	CM Number	Medication	Medication Start Day	Medication End Day	Indication	Taken for an AE? (AE Description; Number)	Taken for a condition on Medical History? (MH Description; Number)	ATC Level 1 (ATC Level 2)

**RESTRICTED**

	SPONSOR: Scandinavian Biopharma Holding AM (SBH)	PROTOCOL NUMBER: OEV-131	PROTOCOL TITLE: Pre-Study of wild type Enterotoxigenic E.coli (ETEC) Strain for Verification of a planned Challenge Dose	VERSION NO: 1.0
				VERSION DATE: 14JUN2024

#### 16.2.7.1 Solicited Events

##### **Listing 11: ETEC Disease-Specific Solicited Events**

Subject ID	Study Day	Assessment Type	Symptom	Severity
		Subjective/Objective		

Notes: Only ETEC disease-specific solicited events that are deemed related to challenge are listed.

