Risks Associated with Antibiotics: Therapeutic antibiotics for use in this study are licensed, approved medications that have been used extensively, and shown to be very safe with only rare side effects. The most commonly reported side effects for ciprofloxacin are gastrointestinal symptoms (nausea, vomiting, and diarrhea) in as many as 5 persons in 100. Other reported symptoms in less than 1 person in 100 include rash, dizziness, and headache. Rarely, allergic reactions to these medications have been observed. Ciprofloxacin is not recommended for use in pregnancy due to concerns of joint damage to the unborn child (based on studies in young animals). Pregnancy is exclusionary for study participation and is documented through testing prior to study interventions and provided discussion on methods to prevent pregnancy during study. Fluoroquinolones, including ciprofloxacin, are associated with an increased risk of tendonitis and tendon rupture in all ages. The risk of developing fluoroquinolone-associated tendonitis and tendon rupture is further increased in older patients, usually over 60 years of age, in patients taking corticosteroid drugs, and in patients with kidney, heart, or lung transplants, all of whom are excluded from this study. *Clostridium difficile*-associated diarrhea (CDAD/ pseudomembranous colitis) has been reported with use of nearly all antibacterial agents.

Subjects will not be discharged until they are well and have had at least two consecutive stool cultures negative for the challenge strain. Both stool cultures may be from the same day. Approximately 6 months after challenge, all subjects will have a follow-up contact by telephone to inquire about the occurrence of any new chronic illnesses or serious adverse events.

Risks Associated with SARS-CoV-2 Exposure and Risk Mitigation: The risk that the COVID-19 pandemic will influence the possibility to perform the study according to plan, or influence the results of the study, will be continuously assessed by the study team. Since the subjects are planned to be enrolled in Q1 2024, when a majority of the adult US population will have been vaccinated or infected with SARS-CoV-2, the risk that the pandemic will have major influence on the study is deemed to be small.

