9.5.3.1.4 ETEC Disease-specific solicited events

ETEC disease-specific solicited events will start being collected after challenge and will be assessed during inpatient physical examinations. Between Challenge and discharge, these pre-defined solicited events will be reported as adverse events and their relationship to the challenge strain, study procedures and/or antibiotics will be determined by the PI or designee.

ETEC Disease-specific subjective solicited events include the following symptoms:

- Malaise
- Loss of appetite
- Headache
- Chills
- Nausea
- Abdominal pain
- Abdominal cramps
- Myalgia
- Arthralgia
- Urgency of defecation
- Lightheadedness

The following solicited events will be documented via objective clinical assessments during the inpatient challenge phase:

1. Diarrhea (via stool logs)
2. Hypovolemia
3. Fever (oral temperature $\geq 100.4^{\circ}\text{ F}$)
4. Vomiting

Table 8. Severity rating of ETEC Disease-specific expected events

Event	Severity ^a	Parameter
Diarrhea, based on highest output of loose ^b stools in any 24-hour period. (A diarrhea episode ends when there is a 24-hour window with no grade 3-5 ^b stools.)	1	Mild: 2-3 loose ^b stools in 24 hours and ≤ 400 grams of loose ^b stools passed in a 24-hour period
	2	Moderate: 4 to 5 loose ^b stools in 24 hours or >400 -800 grams of loose ^b stools passed in a 24-hour period
	3	Severe: 6 or more loose ^b stools in 24 hours or >800 grams of loose ^b stools passed in a 24-hour period
	4	Potentially life-threatening
Fever ^c	1	$100.4^{\circ}\text{F}-101.1^{\circ}\text{F}$ ($38.0-38.4^{\circ}\text{C}$)
	2	$101.2^{\circ}\text{F}-102.0^{\circ}\text{F}$ ($38.5-38.9^{\circ}\text{C}$)
	3	$102.1^{\circ}\text{F}-104^{\circ}\text{F}$ ($39.0-40.0^{\circ}\text{C}$)
	4	$>104^{\circ}\text{F}$ ($>40.0^{\circ}\text{C}$)
Vomiting	1	One episode within a 24-hour period
	2	Two episodes within a 24-hour period
	3	More than two episodes within a 24-hour period
	4	Potentially life-threatening consequence of emesis

^a1=mild; 2=moderate; 3=severe 4=potentially life-threatening.

^bGrades 3-5 stools are considered loose

^cOral temperature; no recent hot or cold beverages, eating or physical activity. If temperature is $\geq 100.4^{\circ}\text{ F}$ every attempt should be made to repeat within 20 minutes. If the repeat temperature is WNL and the investigator feels the repeated temperature is a more accurate reflection of the participant's real temperature a fever will not be entered into the eCRF.

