**RESTRICTED**

	SPONSOR: Scandinavian Biopharma Holding AM (SBH)	PROTOCOL NUMBER: OEV-131	PROTOCOL TITLE: Pre-Study of wild type Enterotoxigenic E.coli (ETEC) Strain for Verification of a planned Challenge Dose	VERSION NO: 1.0

and discharge, these pre-defined solicited events will be reported as adverse events, with severity reported by subjects and relationship to the challenge strain, study procedures, and/or antibiotics determined by the PI or designee.

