## 7.3. ETEC Disease-Specific Solicited Events

Number and percentage of subjects experiencing ETEC disease-specific solicited events are presented by symptom with 95% confidence intervals in [Table 22](#), and by symptom and maximum severity in [Table 23 and Figure 5](#). Number and percentage of subjects experiencing ETEC disease specific solicited events by Study Day are presented in [Table 24](#).

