#### 14.3.1.1 Solicited Adverse Events

**Table 22: Number and Percentage of Subjects Experiencing ETEC Disease-Specific Solicited Events with 95% Confidence Intervals by Symptom - Full Analysis Set**

Sign or Symptom	All Subjects (N=X)		
	n	%	95% CI a
Any Sign or Symptom	x	xx	x.X, x.X
Malaise			
Loss of Appetite			
Headache			
Chills			
Nausea			
Abdominal Pain			
Abdominal Cramps			
Myalgia			
Arthralgia			
Urgency of Defecation			
Lightheadedness			
Diarrhea			
Hypovolemia			
Fever			
Vomiting			

Notes: N = Number of subjects in the Full Analysis Set; n = Number of subjects reporting the corresponding sign or symptom.

a Exact binomial confidence interval calculated using Clopper-Pearson methodology.

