**RESTRICTED**

SPONSOR: Scandinavian Biopharma Holding AM (SBH)	PROTOCOL NUMBER: OEV-131	PROTOCOL TITLE: Pre-Study of wild type Enterotoxigenic E.coli (ETEC) Strain for Verification of a planned Challenge Dose	VERSION NO: 1.0
			VERSION DATE: 14JUN2024

**Table 23: Number and Percentage of Subjects Experiencing ETEC Disease Specific Solicited Events by Symptom and Maximum Severity - Full Analysis Set**

Sign or Symptom	Severity	All Subjects (N=X)	
		n	%
Any Sign or Symptom	None	x	xx
	Mild	x	xx
	Moderate	x	xx
	Severe	x	xx
	Potentially Life-Threatening	x	xx
Malaise	None		
	Mild		
	Moderate		
	Severe		
	Potentially Life-Threatening		
Loss of Appetite	None		
	Mild		
	Moderate		
	Severe		
	Potentially Life-Threatening		
[Continue with remaining solicited symptoms...]	None		
	Mild		
	Moderate		
	Severe		
	Potentially Life-Threatening		

Notes: N = Number of subjects in the Full Analysis Set. n = Number of subjects with reported event. Severity is the maximum severity reported over all solicited symptoms post challenge for each subject.

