**RESTRICTED**

	SPONSOR: Scandinavian Biopharma Holding AM (SBH)	PROTOCOL NUMBER: OEV-131	PROTOCOL TITLE: Pre-Study of wild type Enterotoxigenic E.coli (ETEC) Strain for Verification of a planned Challenge Dose	VERSION NO: 1.0
				VERSION DATE: 14JUN2024

**Table 24: Number and Percentage of Subjects Experiencing Solicited Events by Symptom, Severity and Days - Full Analysis Set**

Sign or Symptom	Severity	Day 1 (N=X)		Day 2 (N=X)		Day 3 (N=X)		Day 4 (N=X)		Day 5 (N=X)		Day 6 (N=X)		Day 7 (N=X)		Day 8 (N=X)		Day 9 (N=X)	
		n	%	n	%	n	%	n	%	n	%	n	%	n	%	n	%	n	%
Any Sign or Symptom	None																		
	Mild																		
	Moderate																		
	Severe																		
	Potentially Life-Threatening																		
	Not Reported																		
Malaise	None																		
	Mild																		
	Moderate																		
	Severe																		
	Potentially Life-Threatening																		
	Not Reported																		
Loss of Appetite	None																		
	Mild																		
	Moderate																		
	Severe																		
	Potentially Life-Threatening																		
	Not Reported																		
[Continue with remaining solicited symptoms...]	None																		
	Mild																		
	Moderate																		
	Severe																		
	Potentially Life-Threatening																		
	Not Reported																		

Notes: N = Number of subjects in the Full Analysis Set; n = Number of subjects with reported event.

Severity is the maximum severity reported post challenge for each subject on each day.

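### Listing 11 drops solicited events not judged related to challenge, so a non-serious solicited event attributed only to antibiotics or procedures reaches no adverse event listing, and Tables 22–24 cannot be rebuilt from it

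*SAP*

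**What the plan says.** **Status of solicited events.** Protocol 9.5.3.1.4 says: "Between Challenge and discharge, these pre-defined solicited events will be reported as adverse events". SAP 2.8.3 repeats this, with "relationship to the challenge strain, study procedures, and/or antibiotics determined by the PI or designee". Causality is therefore assessed for each solicited event against three possible causes.

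**Tables.** SAP 7.3 states: "Number and percentage of subjects experiencing ETEC disease-specific solicited events are presented by symptom with 95% confidence intervals". The note to Table 22 defines "n = Number of subjects reporting the corresponding sign or symptom". The note to Table 23 reads "Severity is the maximum severity reported over all solicited symptoms post challenge for each subject", and the note to Table 24 reads "Severity is the maximum severity reported post challenge for each subject on each day". None mentions relationship. Table 24 runs from Day 1 to Day 9, which includes the routine antibiotic start on Day 6.

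**Listing.** The note to Listing 11 reads "Only ETEC disease-specific solicited events that are deemed related to challenge are listed". Its columns are subject, study day, assessment type, symptom and severity.

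Table numbers here follow SAP 7.3, SAP 7.4 and the mock-up titles. The list of tables in Appendix A numbers the same tables one higher.

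**The concern.** A listing should let a reader trace every count in the table it supports. Here the listing is filtered on a judgement that the tables do not mention and the listing does not display. A reader who finds more subjects in Table 22 than in Listing 11 could not tell whether the excess is a programming error or events attributed to another cause.

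The second issue is completeness. Every subject takes a 3-day antibiotic course, starting on Day 6 or sooner, while solicited collection continues to discharge. Protocol 7.3.2 says ciprofloxacin causes "gastrointestinal symptoms (nausea, vomiting, and diarrhea) in as many as 5 persons in 100", and all three are solicited terms. The same section names lightheadedness, also a solicited term, as a possible effect of blood sampling, and exploratory samples are drawn on Days 3, 4 and 8. Attribution to antibiotics or procedures is thus foreseeable. It is collected for solicited events, but for the non-serious ones no planned output shows it.

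**Working it through.** The plan gives no figure on this point to reproduce. The check is a trace through the outputs, followed by a bound on the size.

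**Step 1. Follow one event.** Take a non-serious solicited event, such as nausea on Day 7, judged related to antibiotics and not to challenge.

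| Output | Scope in the SAP | Event shown with its cause? |
|---|---|---|
| Listing 11 | Solicited, challenge-related only | No, excluded |
| Listing 12 | Unsolicited only; has the three relationship columns | No |
| Listing 13 | Serious events only; has the three relationship columns | No |
| Table 21, solicited row | Any solicited event, split by severity | Counted, cause not shown |
| Table 21, antibiotic and procedure rows | Unsolicited only | No |
| Tables 22–24 | Solicited, no stated filter | Counted if no filter applies; cause not shown |
| Table 26 and Figures 8–9 | Unsolicited only, relationship to challenge | No |
| Listings 6 and 7 | Loose stools; severity score components | Raw data only, no causality |

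**Step 2. Compare with the plan's own rules.**
- SAP 3.1.2 sets a general convention that all subject-level data are listed.
- SAP 7.4 says every reported adverse event enters the summaries and analyses, and describes Listing 11 as a listing of subjects with solicited events, without restriction.
- Protocol 9.7.3.1 requires adverse events to be tabulated by severity and by relationship to the test product. Solicited events are adverse events, yet no table shows their relationship even to challenge.

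The Listing 11 note departs from the first two rules. The tables fall short of the third.

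**Step 3. Try each reading of the tables' silence.**
- Tables 22–24 count all solicited events: the Day 7 nausea is in the tables and absent from Listing 11, so the two do not reconcile.
- Tables 22–24 carry the same filter as Listing 11: they reconcile, but the event is missing from those tables too, against SAP 7.4.
- Unrelated solicited symptoms are re-recorded as unsolicited: the event reaches Listing 12 and the antibiotic row, and the gap closes. Neither document states this rule.

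The gap in the listings and in the two Table 21 rows remains under the first two readings.

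**Step 4. Size in Table 22.** Enrolment is 25 to 30 (protocol 9.3.4). One added subject changes a percentage by 1/30 = 3.3 points or 1/25 = 4.0 points. As an illustration with an assumed count, 9/30 = 30% (Clopper-Pearson 95% CI 14.7 to 49.4) becomes 10/30 = 33% (17.3 to 52.8). A subject is counted once per symptom, so the change occurs only if that subject had not already reported it.

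For diarrhea this can be bounded roughly. Assume that the whole 5 in 100 is diarrhea, that it is independent of ETEC illness, and that 80% of subjects already have diarrhea (the lowest overall attack rate for this lot in protocol Table 3, which ranges from 80% to 100%).
- Chance per subject: 0.05 × 0.20 = 0.01.
- Expected added subjects: 0.01 × 25 = 0.25 to 0.01 × 30 = 0.30.
- Chance of at least one: 1 − 0.99^25 = 22% to 1 − 0.99^30 = 26%.
- At a 100% attack rate the addition is zero.

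The documents give no separate side-effect rates for nausea and vomiting.

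**The case against.** The strongest reply is that the tables are silent, and that the Listing 11 note may reflect a working convention: a symptom counts as a solicited ETEC event only when challenge-related and is otherwise handled as unsolicited. Table 21, which splits only unsolicited events by cause, fits that convention. It cannot be excluded, but it is not written down, and SAP 2.8.3 provides for events to be related to antibiotics or procedures while still solicited. If the convention exists, the SAP needs to state it.

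A reader might also infer that antibiotic side effects are counted as ETEC disease and inflate the symptom rates. The documents do not support that. The absence of a filter in Tables 22–24 is inferred from silence. Table 22 counts subjects reporting a sign or symptom and attributes nothing to ETEC, and a side effect adds to it only as that subject's first occurrence of the symptom.

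Nor does the 5 in 100 figure measure inflation. Applied to 25 to 30 subjects it gives 1.25 to 1.5 expected, and a 72% to 79% chance of at least one. That is the chance of any ciprofloxacin gastrointestinal effect at the protocol's upper figure, whatever symptoms the subject already had and whatever cause the investigator assigns.

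Three further limits stand. An event judged related to both challenge and antibiotics stays in Listing 11. Listings 6, 7 and 10 show stool data, score components and antibiotic dates, so much of the raw information survives. The named safety endpoints, serious adverse events and events leading to withdrawal, have their own outputs (Listing 13 and Table 27), whose titles are not limited to unsolicited events.

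**Conclusion.** The point holds as a reporting gap. The Listing 11 filter is explicit and conflicts with the SAP's own listing and adverse event rules. Followed as written, a non-serious solicited event attributed only to antibiotics or procedures appears in no adverse event listing and in neither matching row of Table 21. Tables 22–24, which state no such restriction, cannot be reproduced from Listing 11.

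This rests on two assumptions: that Tables 22–24 mean what they say in stating no filter, and that no unstated rule moves such events to the unsolicited category. The affected items are the safety reporting and one descriptive secondary endpoint, the occurrence of ETEC disease-specific events. The adjudicated primary endpoint is unaffected: the committee decides attribution to ETEC, and qualifying episodes must begin within 120 hours of challenge. The change to any Table 22 rate is probably small, at 3.3 to 4.0 percentage points per newly counted subject. The correction is worth making because the planned safety output is otherwise incomplete.

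**What to change.** 1. Delete the relatedness note from Listing 11 and add the three relationship columns already in Listing 12 (challenge, study procedure, antibiotics).
2. Extend the antibiotic-related and procedure-related rows of Table 21 to include solicited events.
3. State in SAP 7.3 and in the notes to Tables 22–24 that all solicited events are counted regardless of relationship. A challenge-related column beside the all-events column in Table 22 would be useful but is optional.
4. If the site does re-record unrelated solicited symptoms as unsolicited events, write that rule into SAP 2.8.3.

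The cost is a SAP revision and changes to a few output shells and programs. Causality is already assessed for every solicited event, so no new data are needed. Listing 11 and Tables 21–24 carry no topline asterisk, so the topline package is not affected.
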